## 6.3 Dose modifications for toxicities

### 6.3.1 Dose modification and dose interruption

For participants who do not tolerate the protocol-specified dosing schedule due to drug related toxicities, dose interruptions and/or reductions are recommended in order to allow participants to continue the study treatment. For the dose escalation part of the study, dose reductions during cycle 1 are only allowed if a DLT is observed and recorded.

Table 6-7 provides recommendations for dose modification and dose interruption (i.e., interruption and re-initiation criteria for nazartinib and capmatinib treatment).

Refer to Table 6-5 and Table 6-6 for recommended dose reduction steps for the Phase II part of the study.

If, due to study drug related toxicity, a participant requires a dose interruption of >21 days from the intended day of the next scheduled dose, then the participant must be discontinued from the study treatment unless described otherwise.

Each participant is only allowed two dose reductions on each drug. In addition, a participant must discontinue treatment with nazartinib and capmatinib if, after treatment is resumed at a lower dose, the toxicity recurs with the same or worse severity.

Exceptions on dose interruptions and modifications can be made on a case by case basis after discussion with Novartis and Investigator.

In exceptional cases, after discussion with Novartis, participants may be allowed to continue treatment or resume treatment with only one of the investigational drugs.

All dose interruptions or modifications must be recorded on the Dosage Administration Record CRF.

In case of study treatment interruption, visit schedule should still be followed and assessments performed as per Table 7-1 and Table 7-2.

After dose modification, re-escalation to a previous dose level is not permitted apart from the exceptional cases described in Table 6-14 and Table 6-15.

Events not included in the study protocol or the reference guidance documents should be managed according to local practices.

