Grade 4 (life-threatening consequences; urgent intervention indicated)	
Omit study treatment until resolved to ≤ grade 2, then resume same dose level of nazartinib and re-evaluate in 7 days, or sooner if clinically indicated
 
 
• If no recurrence of grade 3 or higher toxicity after 7 days of nazartinib monotherapy, resume capmatinib at ↓ 1 dose level
 
• If recurrence of grade 3 or higher toxicity during nazartinib monotherapy, omit study treatment until resolved to ≤ grade 2, then resume at ↓ 1 dose level of nazartinib.
 
• If no recurrence of grade 3 or higher toxicity after 7 days of nazartinib monotherapy at ↓ 1 dose level, resume capmatinib at ↓ 1 dose level
 

RENAL	
Serum creatinine	
Grade 1 (> ULN - 1.5 x ULN)	Maintain dose levels of nazartinib and capmatinib
Grade 2 (> 1.5 and ≤ 3.0 x baseline; or > 1.5 and ≤ 3 x ULN)	Omit study treatment until resolved to ≤ grade 1 or baseline, then resume treatment at the same dose level of nazartinib and capmatinib
Grade 3 (> 3.0 x baseline; or > 3.0 and ≤ 6.0 x ULN)	Omit study treatment until resolved to ≤ grade 1, then resume nazartinib at the same dose level:

Worst toxicity CTCAE a Grade (value)	Recommendation
	
 
• If no recurrence of grade 3 toxicity after 7 days of nazartinib monotherapy, resume capmatinib at ↓ 1 dose level
 
• If recurrence of grade 3 toxicity on maintained dose of nazartinib and ↓ 1 dose level of capmatinib, omit study treatment until resolved to ≤ grade 1, then resume nazartinib at same dose level and Capmatinib ↓ 1 dose level
 
• If recurrence of grade 3 toxicity during nazartinib monotherapy, omit study treatment until resolved to ≤ grade 1 or baseline, then resume nazartinib ↓ 1 dose level
 
• If no recurrence of grade 3 toxicity after 7 days of nazartinib monotherapy at ↓ 1 dose level, resume capmatinib at ↓ 1 dose level
 

Grade 4 (> 6.0 × ULN)	Discontinue capmatinib permanently and omit nazartinib until resolved to ≤ grade 1 or baseline, then resume nazartinib at same dose level.
HEPATICb	
Isolated Total Bilirubin elevation (for participants with Gilbert Syndrome these dose modifications apply to changes in direct [conjugated] bilirubin only)	
Grade 1 (> ULN – 1.5 × ULN)	Maintain nazartinib and capmatinib dose level

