Grade 2 (> 1.5 and ≤ 3.0 × ULN)	Omit study treatment. Monitor LFTs c weekly, or more frequently if clinically indicated until resolved to ≤ grade 1, then resume nazartinib and capmatinib at the same dose level.
Grade 3 (> 3.0 and ≤ 10.0 × ULN) g	
Omit study treatment. Monitor LFTsc weekly, or more frequently if clinically indicated until resolved to ≤ grade 1, then resume nazartinib at the same dose level.
 
 
• If no recurrence of grade 3 toxicity after 7 days of nazartinib monotherapy, resume capmatinib at ↓ 1 dose level
 
• If recurrence of grade 3 toxicity on maintained dose level of nazartinib and ↓ 1 dose level of capmatinib, omit study treatment until resolved to ≤ grade 1, then resume nazartinib at same dose level and Capmatinib ↓ 1 dose level
 
• If recurrence of grade 3 toxicity during nazartinib monotherapy, omit study treatment until resolved to ≤ grade 1, then resume nazartinib at ↓ 1 dose level
 
• If no recurrence of grade 3 toxicity after 7 days of nazartinib monotherapy at ↓ 1 dose level, resume capmatinib at ↓ 1 dose level
 

Grade 4 (> 10.0 × ULN) g	
Discontinue participant permanently from capmatinib and nazartinib.
 
The participant should be monitored weekly (including LFTsc), or more frequently if clinically indicated, until total bilirubin has resolved to baseline or stabilization over 4 weeks.

Isolated AST or ALT elevation	
Grade 2 (> 3.0 and ≤ 5.0 × ULN)	
Maintain dose level of both drugs with LFTsc monitored per protocol.
 
Repeat LFTsc as soon as possible, preferably within 48-72 hours from awareness of the abnormal results; if abnormal lab values are confirmed upon the repeat test, then monitor LFTsc weekly, or more frequently if clinically indicated, until resolved to ≤ grade 1.

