g Note: If total bilirubin > 3.0 × ULN is due to the indirect (non-conjugated) component only, and hemolysis as the etiology has been ruled out as per institutional guidelines (e.g., review of peripheral blood smear and haptoglobin determination), then ↓ 1 dose level and continue treatment at the discretion of the investigator. h A CT scan or other imaging study to assess the pancreas, liver, and gallbladder must be performed within 1 week of the first occurrence of any ≥ grade 3 of amylase and/or lipase. If asymptomatic grade 2 elevations of lipase and/or amylase occur again at the reduced dose, participants will be discontinued permanently from study treatment. i Antidiarrheal medication is recommended at the first sign of abdominal cramping, loose stools or overt diarrhea. j During the whole duration of treatment with capmatinib, the participant is recommended to use precautionary measures against ultraviolet exposure (e.g., use of sunscreen, protective clothing and avoid sunbathing or using a solarium intensively).	

**Table 6-8 Dose modifications for capmatinib monotherapy (or if nazartinib permanently discontinued and capmatinib continued as monotherapy)**

Worst toxicity CTCAE Grade a during a cycle of therapy	Recommendation
No toxicity	Maintain dose level
HEMATOLOGICAL	
Neutrophil count decreased (ANC) Neutropenia	
Grade 1 (ANC < LLN - 1500/mm  ; < LLN - 1.5 x 10  /L)	Maintain dose level
Grade 2 (ANC < 1500 - 1000/mm  ; < 1.5 - 1.0 x 10  /L)	Maintain dose level
Grade 3 (ANC < 1000 - 500/mm  ; < 1.0 - 0.5 x 10  /L)	Omit dose until resolved to ≤ grade 2, then: 
 
• If fully resolved in ≤ 7 days, resume treatment at the same dose level
 
• If fully resolved in > 7 days, then resume at ↓ 1 dose level
 

Grade 4 (ANC < 500/mm  ; < 0.5 x 10  /L)	Omit dose until resolved to ≤ grade 2 and then resume at ↓ 1 dose level
Platelet count decreased (Thrombocytopenia)	
Grade 1 (PLT < LLN - 75,000/mm  ; < LLN - 75 x 10  /L)	Maintain dose level
Grade 2 (PLT < 75,000 - 50,000/mm  ; < 75 - 50 x 10  /L)	Maintain dose level

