Grade 3 (PLT < 50,000 - 25,000/mm  ; < 50 - 25 x 10  /L)	Omit dose until resolved to ≤ grade 2, then: 
 
• If fully resolved in ≤ 7 days, then resume at same dose level
 
• If resolved in > 7 days, then resume at ↓ 1 dose level
 

Grade 4 (PLT < 25,000/mm  ; < 25 x 10  /L)	Omit dose until resolved to ≤ grade 2, then resume at ↓ 1 dose level
Febrile Neutropenia	
ANC < 1000/mm  and a single temperature of >38.3°C (101°F) or a sustained temperature of ≥38°C (100.4°F) for more than one hour	Omit dose, then: 
 
• If resolved in ≤ 7 days, resume treatment at resume at ↓ 1 dose level
 
• If resolved in > 7 days, permanently discontinue capmatinib treatment
 

Hemoglobin decreased (Anemia)	
Grade 1 (Hemoglobin [Hgb] < LLN - 10.0 g/dL; < LLN - 6.2 mmol/L; < LLN - 100 g/L)	Maintain dose level

Worst toxicity CTCAE Gradea during a cycle of therapy	Recommendation
Grade 2 (Hgb < 10.0 - 8.0 g/dL; < 6.2 – 4.9 mmol/L; < 100 - 80 g/L)	Maintain dose level
Grade 3 (Hgb < 8.0 g/dL; < 4.9 mmol/L; < 80 g/L; transfusion indicated)	Omit dose until resolved to ≤ grade 2, then: 
 
• If fully resolved in ≤ 7 days, resume at the same dose level
 
• If fully resolved in > 7 days, then resume at ↓ 1 dose level
 

Grade 4 (Life-threatening consequences; urgent intervention indicated)	Omit dose until resolved to ≤ grade 2 and then resume at ↓ 1 dose level If grade 4 toxicity recurs, permanently discontinue capmatinib treatment.
RENAL	
Serum creatinine	
Grade 1 (> ULN - 1.5 x ULN)	Maintain dose level
Grade 2 (> 1.5 - 3.0 x ULN)	Omit dose until resolved to ≤ grade 1 or baseline, then resume at the same dose level.
Grade 3 (> 3.0 - 6.0 x ULN)	Omit dose until resolved to ≤ grade 1 or baseline, then resume at ↓ 1 dose level.
Grade 4 (> 6.0 x ULN)	Permanently discontinue capmatinib treatment
HEPATIC	
Isolated Total Bilirubin elevation*	
Grade 1 (> ULN - 1.5 x ULN)	Maintain dose level
Grade 2 (> 1.5 - 3.0 x ULN)	Omit dose until resolved to ≤ grade 1, then 
 
• If fully resolved in ≤ 7 days, resume at same dose level.
 
• If resolved in > 7 days, resume at ↓ 1 dose level
 

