Grade 3 (> 3.0 - 10.0 x ULN)	Omit dose until resolved to ≤ grade 1, then 
 
• If fully resolved in ≤ 7 days, resume at ↓ 1 dose level
 
• If fully resolved in > 7 days, permanently discontinue capmatinib treatment
 

Grade 4 (> 10.0 x ULN)	Mandatory: Permanently discontinue capmatinib treatment
Isolated AST or ALT elevation	
Grade 1 (> ULN - 3 x ULN)	Maintain dose level
Grade 2 (> 3.0 - 5.0 x ULN)	Maintain dose level
Grade 3 (> 5.0 - 20.0 x ULN)	Omit dose until resolved to ≤ grade 1 (or ≤ grade 2 if grade 2 elevation at baseline) then 
 
• If fully resolved in ≤ 7 days, then resume at the same dose level
 
• If fully resolved in > 7 days, resume at ↓ 1 dose level
 

Grade 4 (> 20.0 x ULN)	Mandatory: Permanently discontinue capmatinib treatment
Combined elevations of AST or ALT and Total Bilirubinb,c,d	
For participants with normal baseline ALT and AST and total bilirubin value: AST or ALT > 3.0 x ULN combined with total bilirubin > 2.0 x ULN without evidence of cholestasis or hemolysis OR For participants with elevated baseline AST or ALT or total bilirubin value:	Mandatory: Permanently discontinue capmatinib treatment

Worst toxicity CTCAE Gradea during a cycle of therapy	Recommendation
[AST or ALT > 3 x baseline] OR [AST or ALT > 8.0 x ULN], whichever is lower, combined with [total bilirubin > 2 x baseline AND > 2.0 x ULN] without evidence of cholestasis or hemolysis	
METABOLIC	
Amylase and/or lipase elevation	
Grade 1 (> ULN - 1.5 x ULN)	Maintain dose level
Grade 2 (> 1.5 - 2.0 x ULN; > 2.0 - 5.0 x ULN and asymptomatic)	Maintain dose level
Grade 3 (> 2.0 - 5.0 x ULN with signs or symptoms; > 5.0 x ULN and asymptomatic)	Omit the dose until resolved to ≤ grade 1, then 
 
• If fully resolved in ≤ 14 days, resume at the same dose level
 
• If fully resolved in > 14 days, then resume at ↓ 1 dose level
 

Grade 4 (> 5.0 x ULN with signs or symptoms)	Permanently discontinue capmatinib treatment
CARDIAC	
Electrocardiogram QT corrected (QTc) interval prolonged	
Grade 1 (QTcF 450-480 ms) Grade 2 (QTcF 481-500 ms)	Maintain dose level

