Grade 1 or 2	Maintain dose level, consider to initiate appropriate support medication. For any intolerable grade 2 (e.g. limiting instrumental activities of daily living), consider omitting the dose until resolved to ≤ grade 1, then resume either at same dose or ↓ 1 dose level.
Grade 3	Omit dose until resolved to ≤ grade 1, then resume at ↓ 1 dose level
Grade 4	Permanently discontinue capmatinib

All dose modifications should be based on the worst preceding toxicity.
 
a Common Toxicity Criteria for Adverse Events (CTCAE version 5.0).
 
b “Combined” defined as: total bilirubin increase to the defined threshold concurrently with ALT/AST increase to the defined threshold
 
c “Cholestasis” defined as: ALP elevation (> 2.0 x ULN and R value (ALT/ALP in x ULN) < 2.0) in participants without bone metastasis, or elevation of ALP liver fraction in participants with bone metastasis
 
d If combined elevations of AST or ALT and total bilirubin do not meet the defined thresholds, please follow the instructions for isolated elevation of total bilirubin and isolated elevation of AST/ALT, and take a conservative action based on the degree of the elevations (e.g. discontinue treatment at the situation when omit dose is needed for one parameter and discontinue treatment is required for another parameter). After all elevations resolve to the defined thresholds that allow treatment re-initiation, re-start the treatment either at the same dose or at one dose lower if meeting a criterion for dose reduction
 
* Note: If total bilirubin > 3.0 x ULN is due to the indirect (non-conjugated) component only, and hemolysis as the etiology has been ruled out as per institutional guidelines (e.g., review of peripheral blood smear and haptoglobin determination), then ↓ 1 dose level and continue treatment at the discretion of the investigator
 
** Note: antidiarrheal medication is recommended at the first sign of abdominal cramping, loose stools or overt diarrhea
 
*** During the whole duration of treatment with capmatinib, the participant is recommended to use precautionary measures against ultraviolet exposure (e.g., use of sunscreen, protective clothing and avoid sunbathing or using a solarium intensively)
	

**Table 6-9 Dose modifications for nazartinib (if capmatinib permanently discontinued and nazartinib continued as monotherapy)**

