Worst toxicity CTCAE a Grade (value) during a cycle of therapy	Recommendations
HEMATOLOGICAL	
Neutrophil count decreased (ANC) Neutropenia	
Grade 1 (ANC <LLN - 1500/mm  )	Maintain dose level
Grade 2 (ANC <1500 - 1000/mm  )	Maintain dose level
Grade 3 (ANC <1000 - 500/mm  )	Omit dose until resolved ≤ Grade 2, then maintain dose level
Grade 4 (ANC <500/mm  )	Recommendation: omit dose until resolved to ≤ Grade 2, then resume at ↓ 1 dose level
Febrile Neutropenia	
(ANC <1.0 x 10  /L, fever ≥ 38.5°C)	Recommendation: omit dose until resolved, then resume at ↓ 1 dose level
Thrombocytopenia	
Grade 1 (PLT <LLN - 75,000/mm  )	May maintain dose level
Grade 2 (PLT <75,000 - 50,000/mm  )	May maintain dose level
Grade 3 (PLT <50,000 - 25,000/mm  )	
 
Recommendation: omit dose until resolved to ≤ Grade 1, then:
 
If fully resolved in ≤ 7 days, then resume at same dose level
 
If fully resolved in >7 days, then resume at ↓ 1 dose level
 

Grade 4 (PLT <25,000/mm  )	Recommendation: omit dose until resolved to ≤ Grade 1, then resume at ↓ 1 dose level
RENAL	
Serum creatinine	
Grade 1 (>ULN - 1.5 x ULN)-	May maintain dose level
Grade 2 (>1.5 – 3.0 x ULN)	Recommendation: omit dose until resolved to ≤ Grade 1 or baseline, then resume at same dose level
Grade 3 (>3.0 – 6.0 x ULN)	Recommendation: omit dose and discontinue nazartinib
Grade 4 (>6.0 x ULN)	Recommendation: omit dose and discontinue nazartinib
HEPATICb	
Isolated Total Bilirubin (for participant s with Gilbert Syndrome these dose modifications apply to changes in direct [conjugated] bilirubin only)	
Grade 1 (>ULN - 1.5 x ULN)	Recommendation: maintain dose level
Grade 2 (>1.5 - 3.0 x ULN)	Recommendation: omit dose. Monitor LFTs c weekly, or more frequently if clinically indicated until resolved to ≤ 1.5 x ULN, then: 
 
If fully resolved in ≤14 days, then resume at same dose level
 
If fully resolved in >14 days, then resume at ↓ 1 dose level
 

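### For an indirect-only bilirubin rise, Tables 6-7, 6-8 and 6-9 interrupt dosing at >1.5–3.0 x ULN but let it continue above 3.0 x ULN, and the Gilbert clause is missing from Table 6-8

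*Protocol*

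**What the plan says.** Section 6.3.1 of the protocol sets out isolated total bilirubin rules in three tables.

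- **Grade 2 rows (>1.5–3.0 x ULN).** Table 6-7 stops both drugs and monitors liver tests "weekly, or more frequently if clinically indicated until resolved to ≤ grade 1, then resume nazartinib and capmatinib at the same dose level". Table 6-8 begins "Omit dose until resolved to ≤ grade 1, then": same dose if recovery takes 7 days or less, one level lower if longer. Table 6-9 stops nazartinib until 1.5 x ULN or below: same dose within 14 days, one level lower after that. None of these rows mentions an indirect-only rise.
- **Footnotes.** Table 6-7 footnote g opens "If total bilirubin > 3.0 × ULN is due to the indirect (non-conjugated) component only" and, once hemolysis has been excluded, ends "then ↓ 1 dose level and continue treatment at the discretion of the investigator". Footnote b of Table 6-7, the asterisk note of Table 6-8 and footnotes b and g of Table 6-9 say the same for Grade 3 or 4 or for values above 3.0 x ULN.
- **Grade 4 rows (>10 x ULN).** Table 6-8 reads "Mandatory: Permanently discontinue capmatinib treatment". Table 6-9 has the corresponding mandatory wording for nazartinib. Table 6-7 also requires permanent discontinuation of both drugs, without that label.
- **Gilbert syndrome.** The bilirubin heading of Table 6-7 states "for participants with Gilbert Syndrome these dose modifications apply to changes in direct [conjugated] bilirubin only", and Table 6-9 carries the same clause. The heading in Table 6-8 carries only the asterisk.
- **General rules.** Discontinuation applies, unless described otherwise, when because of drug-related toxicity "a participant requires a dose interruption of >21 days from the intended day of the next scheduled dose". Each drug may be reduced twice, and re-escalation is barred except in cases described in the rash tables (6-14 and 6-15).

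**The concern.** The exception for an indirect-only rise begins at 3.0 x ULN, so the band just below it falls back on the ordinary Grade 2 rule, which stops drug. Two participants with the same benign-pattern rise are then handled differently, and the one with the lower value is the one interrupted. At the top of the range a site meets a mandatory stop in the row and permission to continue in the note, with nothing saying which governs. For Gilbert syndrome, the heading of Tables 6-7 and 6-9 exempts an indirect rise from modification, the notes to the same rows prescribe a reduction for an indirect rise without mentioning Gilbert, and Table 6-8 is silent.

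Two things are at stake. These are site-level instructions for hepatic toxicity and should be followed alike everywhere. Also, Table 3-1 makes dose interruptions, reductions and dose intensity the tolerability endpoints, including for Group 5. If sites resolve the gaps differently, those endpoints will partly record how the tables were read.

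**Working it through.** No sample-size, power or event figure is involved, so the check applies each row and note to the same hypothetical participant: an isolated, indirect-only rise, hemolysis ruled out. The inputs are the bilirubin rows, headings and notes of Tables 6-7, 6-8 and 6-9 and the general rules of Section 6.3.1.

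**Without Gilbert syndrome**

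| Value | Table 6-7 (combination) | Table 6-8 (capmatinib alone) | Table 6-9 (nazartinib alone) |
|---|---|---|---|
| 2.5 x ULN | Both drugs stopped, then same doses | Stopped; same dose if ≤7 days, one level lower if >7 days | Stopped; same dose if ≤14 days, one level lower if >14 days |
| 3.5 x ULN, under the note | One level lower, dosing may continue | One level lower, dosing may continue | One level lower, dosing may continue |
| >10 x ULN, under the row | Permanent stop | Permanent stop, marked mandatory | Permanent stop, marked mandatory |
| >10 x ULN, under the note | One level lower, dosing may continue | One level lower, dosing may continue | One level lower, dosing may continue |

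1. *Interruption.* In all three tables 2.5 x ULN interrupts and 3.5 x ULN need not.
2. *Dose level.* In Table 6-8, a Grade 2 rise that needs more than 7 days gives an interruption plus a one-level reduction; above 3.0 x ULN the note gives the same reduction without the interruption. Table 6-9 behaves the same way after 14 days. Table 6-7 differs: Grade 2 resumes at full dose, whereas the note costs a level that Section 6.3.1 does not let the participant regain. There the ordering is reversed for interruption only.
3. *Persistence.* If a Grade 2 rise is judged drug related and the interruption exceeds 21 days, Section 6.3.1 leads to discontinuation unless described otherwise. The path above 3.0 x ULN need not start that clock.
4. *Grade 4.* The markers tie the note to the Grade 4 row (g in Tables 6-7 and 6-9) or to the whole bilirubin block (asterisk in Table 6-8), but no sentence says that it overrides a row marked mandatory.

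**With Gilbert syndrome**

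| Value | Tables 6-7 and 6-9 | Table 6-8 |
|---|---|---|
| 2.5 x ULN | No modification, under the heading | Stopped until recovery |
| 3.5 x ULN | No modification if the heading governs the note; one level lower if it does not | One level lower, dosing may continue |

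5. Under Tables 6-7 and 6-9 the heading removes the Grade 2 interruption, so the reversal does not reach these participants. What remains open is whether the heading also governs the note.
6. Under Table 6-8 the reversal does reach them. Group 5 starts on capmatinib alone and may move to the combination at radiological progression, so the same Gilbert participant at 2.5 x ULN is interrupted in the first period and left unmodified in the second. Exclusion criterion 17 keeps out Group 5 participants above 1.5 x ULN, so the situation arises after entry.

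**The case against.** The strongest reply is that these entries are not rigid. Section 6.3.1 calls Table 6-7 a set of recommendations, Table 6-9 labels its Grade 2 action a recommendation, and exceptions can be agreed case by case between sponsor and investigator. The 21-day rule covers only drug-related toxicity. This softens the consequence, but a discussion about one participant does not make the printed tables agree.

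Several stronger readings are tempting, and the protocol does not support them:

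- *The footnote contradicts the Gilbert heading.* The notes do not mention Gilbert syndrome and sit on rows under that heading, so they can be read as serving everyone else. The two are unreconciled, not contradictory.
- *Two incompatible orders apply above 10 x ULN.* The markers can be read as linking an exception to its rule. The fault is that precedence over a mandatory row is not stated.
- *The lower value always has the more severe action.* This is true of interruption. It is not true of the resumed dose in Table 6-7, nor for Gilbert participants under Tables 6-7 and 6-9. The note also depends on excluding hemolysis and on investigator discretion.
- *Group 5 response rate is lowered.* One participant weighs 1/10 = 10 percentage points in Stage 1 and 1/30 = 3.3 points of 30. That is a weight, not an effect. No frequency of such rises is given, an interruption does not turn a responder into a non-responder, and Section 6.3.1 keeps scheduled assessments running during it.
- *Reconciling needs no further tests.* The liver-test notes of Tables 6-7 and 6-9 call for fractionation only above 2.0 x ULN, and those of Table 6-8 do not define liver tests.

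**Conclusion.** The point holds as a wording inconsistency in three tables. For an isolated indirect-only rise with hemolysis excluded, >1.5–3.0 x ULN stops drug and >3.0 x ULN allows it to continue one level lower. In Table 6-8 a slow Grade 2 recovery brings both the interruption and the same reduction. Precedence of the note over the mandatory >10 x ULN rows is unstated. The Gilbert clause is unreconciled with the notes and missing from the table under which Group 5 begins.

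No numerical size can be given, because the protocol gives no rate of indirect-only rises or of Gilbert syndrome, and no effect on response rate is claimed. The consequence is inconsistent hepatic management and some inconsistency in reported interruptions, reductions and dose intensity. The conclusion assumes that sites apply the tables as printed, without an agreed exception. The protocol should be corrected at its next amendment. This review takes no position on which action is clinically right.

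**What to change.** In Section 6.3.1:

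1. Reconcile the Grade 2, 3 and 4 isolated-bilirubin rows with the indirect-only notes in Tables 6-7, 6-8 and 6-9.
2. State whether the note overrides the >10 x ULN rows marked mandatory in Tables 6-8 and 6-9, and likewise the permanent stop in Table 6-7.
3. State whether the Gilbert clause governs the notes in Tables 6-7 and 6-9, and whether it applies to Table 6-8.

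The content of each rule, and whether it should differ between the drugs, is for the sponsor to decide clinically.

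The cost is a wording change in three tables. If the sponsor chooses to extend the exception to Grade 2, bilirubin fractionation between 1.5 and 2.0 x ULN, a fractionation rule for Table 6-8, and a hemolysis work-up at Grade 2 may be needed.

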## **6 Treatment**

### **6.1 Study treatment**

The investigational drugs to be used in this study are nazartinib and capmatinib.

The study treatment is the combination of nazartinib (once a day) and capmatinib (twice a day).

In Phase II Group 5, the participants will start with capmatinib monotherapy (twice a day) and then will have the opportunity to continue with the combination of nazartinib (once a day) and capmatinib (twice a day) based on radiological disease progression evaluation based on investigator's assessment per RECIST 1.1.

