
All dose modifications should be based on the worst preceding toxicity.
 
a Common Terminology Criteria for Adverse Events (CTCAE) version 5.0
 
b If grade 3 or 4 hyper-bilirubinemia is due to the indirect (non-conjugated) component only, and hemolysis as the etiology has been ruled out as per institutional guidelines (e.g., Review of peripheral blood smear and haptoglobin determination), then ↓ 1 dose level and continue treatment at the discretion of the investigator.
 
c LFTs include albumin, ALT, AST, total bilirubin (fractionated if total bilirubin > 2.0 × ULN), alkaline phosphatase (fractionated if alkaline phosphatase > 2.0 × ULN) and gamma-glutamyl transpeptidase (GGT). For isolated elevations of any grade of alkaline phosphatase and/or GGT, maintain dose level.
 
d “Combined” defined as: total bilirubin increases to the defined threshold concurrently with ALT/AST increase to the defined threshold
 
e “Cholestasis” defined as: ALP elevation (> 2 × ULN and R value < 2) in participants without bone metastasis, or elevation of ALP liver fraction in participants with bone metastasis Note: The R value is calculated by dividing the ALT by the ALP, using multiples of the ULN for both values. It denotes the relative pattern of ALT and/or ALP elevation is due to cholestatic or hepatocellular liver injury
 
f If combined elevations of AST or ALT and total bilirubin do not meet the defined thresholds, please follow the instructions for isolated elevation of total bilirubin and isolated elevation of AST/ALT, and take a conservative action based on the degree of the elevations (e.g. discontinue treatment at the situation when omit dose is needed for one parameter and discontinue treatment is required for another parameter). After all elevations resolve to the defined thresholds that allow treatment re-initiation, re-start the treatment either at the same dose or at one dose lower if meeting a criterion for dose reduction
	

Worst toxicity CTCAE a Grade (value)	Recommendation

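### Tables 6-7, 6-8 and 6-9 define creatinine Grades 2 and 3 differently for one CTCAE version, so with a baseline below the ULN one value can call for different dose actions

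*Protocol*

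**What the plan says.** All the rows in question are in Protocol Section 6.3.1, under renal toxicity, serum creatinine.

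- **Table 6-7 (combination).** Grade 1 is "Grade 1 (> ULN - 1.5 x ULN", with both dose levels maintained. Grade 2 is "Grade 2 (> 1.5 and ≤ 3.0 x baseline; or > 1.5 and ≤ 3 x ULN", with the instruction "Omit study treatment until resolved to ≤ grade 1 or baseline, then resume treatment at the same dose level" for both drugs. Grade 3 is "Grade 3 (> 3.0 x baseline; or > 3.0 and ≤ 6.0 x ULN"; both drugs are omitted, and capmatinib comes back one dose level lower.
- **Table 6-8 (capmatinib alone).** Every grade uses the ULN only. Grade 1 means maintain. Grade 2, above 1.5 and up to 3.0 x ULN, means omit and then resume at the same dose. Grade 3 is "Grade 3 (> 3.0 - 6.0 x ULN", and treatment resumes one level lower.
- **Table 6-9 (nazartinib alone).** The cut-offs are the same ULN-only ones. Grade 2 means omit and resume at the same dose. Grade 3 reads "Recommendation: omit dose and discontinue nazartinib".

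Table 6-7 footnotes its grades to "Common Terminology Criteria for Adverse Events (CTCAE) version 5.0"; Tables 6-8 and 6-9 cite the same version. In the creatinine rows of Tables 6-8 and 6-9, baseline appears only as a recovery condition, never in the definition of a grade.

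Section 6.1 explains what is omitted under Table 6-7: "The study treatment is the combination of nazartinib (once a day) and capmatinib (twice a day". Sections 4.1, 6.1.1 and 6.1.2 have Group 5 start on capmatinib alone, with the option of adding nazartinib at radiological progression. Table 3-1 lists interruptions, reductions and dose intensity as the Group 5 tolerability endpoints for monotherapy and for the combination.

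**The concern.** A toxicity grade from one CTCAE version should not depend on which table the site has open. If the two regimens need different handling, the recommendation column is where the difference belongs. Here the definition of the grade differs, and the grade decides whether a dose is maintained, omitted, reduced or stopped.

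The grade also carries forward. Section 6.3.1 allows two reductions per drug, requires discontinuation after a drug-related interruption of more than 21 days unless described otherwise, and requires it when a toxicity recurs at the same or worse severity after resuming at a lower dose.

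Group 5 is where this is live. One participant can be graded by the ULN alone in the first period and by baseline or ULN in the second. Renal interruptions and reductions recorded in the two periods would then rest on different triggers.

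**Working it through.** **Inputs.** The cut-offs are those printed in Tables 6-7, 6-8 and 6-9. Let V be creatinine and b the baseline, both in multiples of the ULN. Where two rows of Table 6-7 fit, the higher grade is taken, following the column heading that refers to the worst toxicity. The documents give no baseline distribution, so the values of b are assumptions, shown as a range.

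**Rules as printed.**
- Table 6-7: Grade 3 if V > 3b or V > 3.0; otherwise Grade 2 if V > 1.5b or V > 1.5; otherwise Grade 1 if V > 1.0. Grade 4 if V > 6.0.
- Tables 6-8 and 6-9: Grade 3 if V > 3.0; otherwise Grade 2 if V > 1.5; otherwise Grade 1 if V > 1.0. Grade 4 if V > 6.0.

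**Where they disagree.**
- Omit (Table 6-7) against maintain (Table 6-8): 1.5b < V ≤ 1.5. This range is empty once b ≥ 1.
- Grade 3 (Table 6-7) against Grade 2 or lower (Tables 6-8 and 6-9): 3b < V ≤ 3.0. Also empty once b ≥ 1.
- Overlap inside Table 6-7, where the Grade 1 row and the Grade 2 or 3 baseline arm both fit: V above the larger of 1.0 and 1.5b, up to 1.5.

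| b | Omit v. maintain (x ULN) | Grade 3 v. Grade 2 or lower (x ULN) | Overlap in Table 6-7 (x ULN) |
|---|---|---|---|
| 0.5 | 0.75–1.5 | 1.5–3.0 | 1.0–1.5 |
| 0.6 | 0.90–1.5 | 1.8–3.0 | 1.0–1.5 |
| 0.7 | 1.05–1.5 | 2.1–3.0 | 1.05–1.5 |
| 0.8 | 1.20–1.5 | 2.4–3.0 | 1.20–1.5 |
| 0.9 | 1.35–1.5 | 2.7–3.0 | 1.35–1.5 |
| 1.0 or more | none | none | none |

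**Single cases.**
- b = 0.6, V = 1.2: V/b = 2.0. Grade 2 in Table 6-7, Grade 1 in Table 6-8.
- b = 0.6, V = 2.0: V/b = 3.33. Grade 3 in Table 6-7, Grade 2 in Tables 6-8 and 6-9.
- Controls: b = 1.0, V = 1.4 is Grade 1 everywhere; b = 1.2, V = 2.0 is Grade 2 everywhere.

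**In laboratory units** (assumed baseline 0.6 mg/dL and ULN 1.2 mg/dL, so b = 0.5). A value of 1.75 gives 1.75/0.6 = 2.92 x baseline and 1.75/1.2 = 1.46 x ULN: omit against maintain. A value of 1.9 gives 1.9/0.6 = 3.17 x baseline and 1.9/1.2 = 1.58 x ULN: Grade 3 against Grade 2, so the dose at which capmatinib resumes differs.

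**The case against.** Four arguments limit this point.

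1. **The tables are recommendations.** Section 6.3.1 recommends interruptions and reductions, and allows case-by-case exceptions after discussion with the sponsor. The creatinine rows are not marked mandatory, although some other rows are. This stands and limits how binding the conflict is. It does not explain two definitions under one CTCAE version.
2. **Table 6-7 is itself unclear.** Its Grade 1 row also fits values above the ULN and up to 1.5 x ULN, so part of the disagreement lies inside that table. This is correct. Only the worst-toxicity heading resolves it, so the overlap belongs in the repair.
3. **The reach is narrow.** The conflict needs a baseline below the ULN. The rationale for Amendment 07 says that nobody in Phase Ib or Groups 1 to 4 is still on treatment. That leaves Group 5, approximately 30 participants. This also stands.
4. **Table 6-4 grades creatinine against baseline too.** This adds little. It is the dose-limiting toxicity definition for Phase Ib, where the RP2D was declared on 23-Feb-2016, and its footnote cites CTCAE 4.03.

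A reader might infer two stronger claims. The first is that an unchanged creatinine becomes a reason to omit both drugs as soon as nazartinib is added. That holds only if baseline in Table 6-7 means the value before monotherapy. If it means the value at the start of the combination, an unchanged creatinine is 1.0 x baseline and the baseline arm is not met. The text available, which ends at the opening of Section 6.3.2, does not say which is meant. The second is that the combination period would show more renal interruptions because of the grading rule alone. No visible passage plans a comparison of interruptions between the periods. The periods also differ in the number of drugs and are separated by progression, and no event rate is given.

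**Conclusion.** The contradiction is established from the tables alone. For one CTCAE version, Table 6-7 defines creatinine Grades 2 and 3 by baseline or ULN, and Tables 6-8 and 6-9 by the ULN only. With a baseline below the ULN, the instruction can differ between maintain and omit, or between resuming at the same dose and at a lower one. In Table 6-9, whether the baseline arm counts can decide between resuming nazartinib and stopping it. The range affected narrows from 0.75–1.5 x ULN at b = 0.5 to 1.35–1.5 at b = 0.9, and vanishes at b = 1.0.

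The size of the effect on Group 5 tolerability data cannot be stated. The documents support saying that the two periods use different triggers, not that one will show an excess. The result assumes that the higher grade governs where two rows of Table 6-7 fit. The CTCAE text is not in the documents, so nothing here says which definition is right. The point is a contradiction worth correcting, with practical effect in Group 5 only.

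**What to change.** Reconcile the creatinine rows of Tables 6-7, 6-8 and 6-9 so that each grade has one definition, matching the CTCAE version cited. Word the Grade 1 row of Table 6-7 so that no value fits it together with a higher grade. If a baseline arm is kept, state which baseline applies once a Group 5 participant moves to the combination. The thresholds and dose actions are for the sponsor to choose. Table 6-4 need not change.

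The cost is the wording of a few rows in up to three tables. Exclusion criterion 17 already needs a creatinine value at entry to calculate clearance, so a pre-treatment baseline requires no new measurement. If the sponsor prefers a baseline at the switch, it should confirm that the Group 5 visit schedule (Table 7-2) provides one.
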